3.3.3. Premature Discontinuation of Investigational Product

Premature discontinuation of the IP by the Investigator is an important discussion that should include the Medical Monitor, if feasible, before the IP is discontinued.

Possible reasons for premature discontinuation from IP due to safety reasons include, but are not limited to, the following:

- Occurrence of an AE that, in the opinion of the Investigator, warrants the patient's permanent discontinuation from IP administration
- Hy's law criteria are met, defined by at least 3-fold elevations of ALT or AST above the ULN, elevation of serum total bilirubin to $>2 \times$ ULN without elevated serum alkaline phosphatase, and no other disease or condition can be found to explain the liver test abnormalities
- Known pregnancy or breastfeeding during the study drug administration period

Possible reasons for discontinuation from the IP *due to insufficient therapeutic effect* include, but are not limited to, clinical worsening or lack of clinical progress. If the Investigator deems the benefit-to-risk ratio of IP continuance acceptable, study drug administration of at least 48 h is encouraged before discontinuation from IP therapy for insufficient effect.

3.3.4. Withdrawal from Study

A patient will be considered to have completed the study when he or she completes the EOT visit for patients in Treatment Arm 4 and the follow-up visit on Day 56 (± 2 days) for patients in Treatment Arms 1, 2, and 3.

Patients may withdraw from the study or be withdrawn at the request of the Investigator or Sponsor at any time. Examples of reasons for study withdrawal include the following:

- The patient withdraws consent or requests withdrawal from the study for any reason
- The patient is lost to follow-up
- The patient fails to comply with protocol requirements or study-related procedures
- The Investigator determines that it is in the best interest of the patient to withdraw from the study protocol for reasons other than an adverse event (AE)
- The study is terminated or temporarily suspended by the Sponsor or a regulatory authority for any reason including, but not limited to, study drug-related unexpected life-threatening serious AEs (SAEs) detected during safety monitoring (e.g., torsade de pointes or other ventricular arrhythmias), and 2 or more of the same drug-related (possible or probable) treatment-emergent SAE

Patients who wish to withdraw completely from this clinical study during the treatment period should be encouraged to undergo the EOT safety and efficacy assessments at the time of withdrawal as shown in the Schedule of Assessments (Table 2). For a patient who agrees to complete the EOT visit, blood draws for PK will not be conducted. In addition, for women of child-bearing potential a pregnancy test should be conducted at this visit. Once a patient withdraws consent, no further data will be collected.

A patient is considered lost to follow-up if he or she fails to return to the study clinic for scheduled visits and is unable to be contacted by the study site. The site must attempt to contact the patient at least twice by phone or letter, and, if no response is obtained from the patient, a certified letter will be sent requesting that the patient contact the Investigator and asking that they return any unused IP and return to the site for a final evaluation. Documentation of these efforts to contact the patient must be recorded in the patient's study file.

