Clinic study visits will occur on Days 1, 7, 14, 21, and 28 (end-of-treatment [EOT] visit) (± 1 day). Patients in the double-blinded Treatment Arms 1, 2, and 3 will be evaluated in a follow-up visit on Day 56 (± 2 days) (28 days after EOT). Patients in the open-label SOC Treatment Arm 4 will be discontinued from the study after the EOT visit.

Baseline symptoms will include chronic cough, fatigue, frequent throat clearing, dyspnea, hemoptysis, excessive mucus (sputum) production, fever, night sweats, loss of appetite, unintended weight loss, wheezing, and chest pain. A multi-dimensional patient-reported outcome (PRO) (see [Appendix 3](#)) instrument assessing severity and changes in these baseline symptoms

will be administered at clinic visits on Days 1, 7, 14, 21, and 28 in all arms and Day 56 in Treatment Arms 1, 2, and 3.

Patient-collected pooled expectorated sputum will be collected on Days –1, 6, 13, 20, and 27 (i.e., the day before clinical study visits over an approximate 24-hour [h] period) for all patients and, for patients in Treatment Arms 1, 2, and 3, on Day 55 (i.e., the day before the follow-up visit on Day 56). In all cases, the patient-collected sputum will be collected on the day before the actual clinic visit. Sputum will also be collected at each clinic visit using a standard induction protocol.

[figure not shown]
Patients in Treatment Arms 1, 2, and 3 will participate in the collection of blood samples for PK analysis as follows:

- At least 3 selected qualifying sites will enroll a total of at least 18 patients (at least 6 per treatment arm) for intensive PK evaluation. On Days 1 and 28, blood samples for intense PK will be collected at pre-dose and post-dose: 1 h, 2 h, 4 h, 8 h, 12 h, and 24 h. On Days 7, 14, and 21, blood samples will be obtained at: pre-dose, 1 h post-dose, and just before discharge from the clinic. The acceptable windows for PK collection are specified in the Schedule of Assessments ([Table 2](#)).
- At all remaining, samples will be collected for sparse PK evaluation, on Days 1, 7, 14, 21, and 28. Blood samples will be obtained at pre-dose, 1 h post-dose, and just before discharge from the clinic.
- Patients randomized to the SOC arm will not participate in PK collection.

Actual dates and times of blood samples as well as dates and times of study drug administration will be recorded. Please refer to the Schedule of Assessments ([Table 2](#)) for allowable windows.

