4.6. Treatment Compliance

All patients will be asked to document in a provided diary the date and time of each IP or SOC dose taken at home, along with other requested information related to IP administration.

Patients will be required to bring the IP wallet the subsequent clinic visit including any remaining capsules that have not been taken. At each visit, the patient's remaining capsules and the diary will be retrieved by the Investigator and compliance assessed.

Investigational product wallets must be returned at each visit, as compliance will be assessed by capsule counts. Investigational product noncompliance for a patient is defined as taking less than 80% or more than 120% of IP during the treatment period (Day 1 through EOT). Discontinuation for noncompliance is at the Investigator's discretion and should be documented accordingly.

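### The plan does not clearly provide off-drug safety follow-up for Arms 1-3 patients who leave during treatment without withdrawing consent

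*Combined protocol and SAP*

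**What the plan says.** Section 3.3.4 (Withdrawal from Study) defines completion in Arms 1-3 as reaching "the follow-up visit on Day 56". It then lists ways of leaving before that. Some do not involve withdrawal of consent: "The patient fails to comply with protocol requirements or study-related procedures" is one, an Investigator's best-interest decision for non-AE reasons is another, and the Sponsor may also withdraw a patient.

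For exit during treatment the section offers one provision: "Patients who wish to withdraw completely from this clinical study during the treatment period should be encouraged to undergo the EOT safety and efficacy assessments". Table 2 footnote b matches it. A patient who terminates early and agrees to the EOT visit has no PK draws, and women of childbearing potential have a pregnancy test then. A separate rule covers consent: "Once a patient withdraws consent, no further data will be collected".

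The planned follow-up is in section 3.1: "Patients in the double-blinded Treatment Arms 1, 2, and 3 will be evaluated in a follow-up visit on Day 56". Section 3.2 places it 28 days after therapy is completed, and footnote c places it 28 (±2) days after EOT. Section 5.4 records AEs from the first dose until the patient's final study event. Section 6.6.3 does not require sites to look for events in people no longer in the study.

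**The concern.** Safety and tolerability is the secondary objective. Section 1.2 reports earlier dosing in healthy volunteers for up to 14 days, whereas this study gives 28 days to patients. The sponsor judged a check 28 days off drug worth having in Arms 1-3, and patients who leave early are the ones not assured of it.

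Section 8.1.9.2 gives TEAEs no end date and reports the percentage of patients with an event at least once during the study. A completer and an early leaver therefore share a denominator, although only the completer is certain to be watched through the off-drug period. A fixed TEAE window at analysis could align the denominators, but it could not recover an event, laboratory change or ECG change that was never collected.

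**Working it through.** No figure in the plan bears on this directly, so the check is mainly a comparison of texts.

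**Who is affected.** Three groups fall outside the point:

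- Patients who withdraw consent, because 3.3.4 ends their data collection.
- Patients who cannot be reached. They are asked to return for a final evaluation, but attendance cannot be assured.
- Patients who only stop study drug under 3.3.3. They are best read as staying on the Table 2 schedule.

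What remains is Arms 1-3 patients who leave the study itself but still consent, by choice or by Investigator or Sponsor decision. The encouraged visit is worded for those who wish to leave; for those who are withdrawn, 3.3.4 names no visit.

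**What is scheduled after exit.**

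- 3.3.4 and footnote b name at most an EOT visit at exit and nothing later.
- 3.2 and footnote c time the follow-up from completion of therapy or from EOT. Neither says whether this applies after an early exit.
- Footnote b adds to the early EOT visit the pregnancy test that Table 2 otherwise places at follow-up. This fits a reading in which no later visit is expected.

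**What is lost if no later visit occurs.** Table 2 and section 5.4 give:

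| Assessment | Attended early EOT visit | Follow-up visit |
|---|---|---|
| Vital signs | yes | yes |
| ECG | yes | yes |
| Urinalysis | yes | yes |
| Safety bloods | yes | yes |
| Pregnancy test, where applicable | yes (footnote b) | yes |
| Physical examination | symptom-directed | full |
| New AEs | up to exit | up to follow-up |

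The loss is the off-drug repeat of the tests, the full examination, and AEs that begin after exit.

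**What is still collected.** Open AEs are followed until resolved or stable (6.7). Unexplained noteworthy laboratory values are followed (5.4). Related SAEs that a site happens to learn of are reported (6.6.3), although that sentence is worded for patients who have completed the study.

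**Size per leaver.** Assume the exit visit falls on the day of the last dose. The unobserved off-drug period is then 28 days, whatever the exit day.

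**Size per arm.** This cannot be derived, because no discontinuation rate is stated. For scale only:

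- Planned patients per arm in Arms 1-3: 72 × 5/19 + 6 = 24.9, so about 75 in all.
- If 5%, 10% or 20% of 75 left in this way (assumed rates), that is 3.75, 7.5 or 15 patients.
- Multiplied by 28 days, that is 105, 210 or 420 patient-days off drug without active collection.
- Take an event with an assumed 10% risk in that window. The chance of seeing at least one in an arm is 1 − 0.9^25 = 0.928 with all 25 patients followed, and 1 − 0.9^20 = 0.878 with 20 followed (the 20% case).

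**The case against.** The strongest reply is that the visit is already there. Section 3.2 gives Arms 1-3 a follow-up after therapy with no exception for early exit, footnote b calls the exit visit the EOT visit, and footnote c counts 28 days from EOT. Read together, these put an early leaver's follow-up about where the fix would. That reading is available, so the documents do not show that the data will certainly go uncollected. It is nowhere stated for patients who have left, however, and 3.3.4, the section a site would consult, stops at exit. Sites could reasonably differ.

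The reply also holds that the group is small and mostly not safety-driven. AE, Hy's law and pregnancy stops sit under study-drug discontinuation in 3.3.3, and the Investigator example in 3.3.4 excludes AEs. In 4.6, "Discontinuation for noncompliance is at the Investigator's discretion" follows a definition of drug compliance and may mean the drug only. This largely stands. Section 8.1.9.2 does plan a listing of study discontinuations due to AEs, so some safety-driven exits are foreseen.

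Finally, attendance cannot be compelled, and the safety analysis is descriptive, so no test is biased. Both are true. They limit what the fix can recover and what is at stake, but they do not supply the missing instruction.

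**Conclusion.** The gap is real but limited. For consenting early leavers in Arms 1-3, the plan does not clearly provide safety observation after exit, and as 3.3.4 reads, about 28 off-drug days per leaver go without active collection of new AEs or repeat tests. The 28 days assume that exit falls on the last-dose day. The number of leavers, and any imbalance between arms, is unknown.

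Three stronger inferences are not supported:

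- A reader might conclude that all six follow-up safety assessments are missed. An attended early EOT visit covers every category, with only the full examination replaced by a symptom-directed one.
- A reader might compare a Day 7 leaver's 7 observed days with a completer's 56 (7/56 = 12.5%). Of the 49 missing days, 21 are treatment days on which the leaver took no drug. The relevant loss is the 28 off-drug days.
- A reader might conclude that patients stopping the drug for an AE are lost. Section 3.3.3 concerns the drug, not the study, and nothing there takes them off the schedule.

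This is a cheap improvement to the safety data, not a flaw that undermines the trial.

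**What to change.** In 3.3.4 and Table 2 footnotes b and c, state that Arms 1-3 patients who leave during treatment and have not withdrawn consent, whether by choice or by Investigator or Sponsor decision, are to have:

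1. an EOT visit at exit; and
2. the existing Table 2 follow-up safety assessments 28 (±2) days after the last dose, with a telephone AE contact if they cannot attend.

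Record new AEs up to that visit or contact.

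The cost is a few sentences of protocol text and one already-planned visit or call per early leaver. Some will not attend, and a call yields AEs but no examination, ECG or laboratory results. Nothing is recovered from patients who withdraw consent or cannot be reached.

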3.3.5. Criteria for Stopping the Study

The Sponsor, in consultation with the Medical Monitor, upon review of available data may stop the study. Possible reasons include, but are not limited to, the following:

- Occurrence of an SAE assessed as probably related to IP and resulting in death
- Occurrence of 2 or more SAEs of the same character that are determined to be clinically significant (CS) and assessed as probably related to IP
- Occurrence of 2 or more AEs of acute pancreatitis, defined as the presence of abdominal pain, elevated pancreatic enzymes (amylase and lipase) $\geq 5 \times$ ULN and determined to be CS, and an abdominal ultrasound with finding consistent with acute pancreatitis
- Occurrence of 2 or more AEs of acute hepatitis meeting Hy's Law criteria, defined by at least 3-fold elevations of ALT or AST above the ULN, elevation of serum total bilirubin to $>2 \times$ ULN without elevated serum alkaline phosphatase, and no other disease or condition can be found to explain the liver test abnormalities

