4. INVESTIGATIONAL PRODUCT

4.1. Identity of the Investigational Product

Investigational product refers to both SPR720 and placebo in this Investigational Product section.

SPR720 will be administered po as 250 mg capsules containing SPR720 as the active substance with no additional excipients. The capsules are white, opaque, size 0, hard gelatin capsules containing a white powder. Placebo doses will also be administered po as white, opaque, size 0, hard gelatin capsules containing an approximately equivalent weight of microcrystalline cellulose (white powder).

SPR720 drug product and placebo are manufactured by Patheon UK Limited (Abingdon, Oxfordshire, UK) under Good Manufacturing Practice conditions and packaged, labeled, and distributed by Almac Clinical Services.

SPR720 and placebo are packaged in blister cards of 28 capsules each and then packaged into wallets that will be given to the patient.

Additional information is provided in the investigator's brochure (IB) and in the Pharmacy Manual.

Standard of care (SOC) will be obtained by the study sites or by prescription. Refer to the Product Package Inserts for detailed information regarding SOC treatments.

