6.2.2. Assessment of Causality

The Investigator (or designee) will make an assessment as to the relationship between the study drug and the occurrence of each AE/SAE. The Investigator (or designee) will use clinical judgment to determine whether the AE/SAE is causally related to the study drug. Alternative causes, such as natural history of the underlying diseases, concomitant therapy, other risk factors, and the temporal relationship of the event to the study drug will be considered and investigated. The Investigator (or designee) will also consult the IB in the determination of his/her assessment.

The causal relationship of the study drug to an AE will be rated according to the following 4-point scale:

- **Unrelated:** Clearly and incontrovertibly due only to extraneous causes and does not meet criteria listed under unlikely, possible, or probable
- **Unlikely:** Does not follow a reasonable temporal sequence from administration; may have been produced by the patient's clinical state or by environmental factors or other therapies administered
- **Possible:** Follows a reasonable temporal sequence from administration; may have been produced by the patient's clinical state or by environmental factors or other therapies administered
- **Probable:** Clear temporal association with improvement on cessation of study drug or reduction in dose; reappears upon rechallenge or follows a known pattern of response to the study drug

There may be situations when an SAE has occurred and the Investigator (or designee) has minimal information to include in the initial report to the Sponsor. However, it is very important that the Investigator (or designee) always assess causality for every event before transmission of the SAE form to the Sponsor. The Investigator (or designee) may change his/her opinion of causality in light of follow-up information, amending the SAE form and the eCRF accordingly. The causality assessment is one of the criteria used when determining regulatory reporting requirements. The Investigator (or designee) will provide an assessment of causality as per instructions on the SAE form.

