6.6.2. Completion and Transmission of the Serious Adverse Event Reports

Once the Investigator (or designee) becomes aware that an SAE has occurred in a study patient, he/she will report the information to the Sponsor (or delegate) and the Sponsor's Medical Monitor within 24 h. The SAE form/eCRF will always be completed as thoroughly as possible with all available details of the event, signed by the Investigator (or designee), and forwarded to the Sponsor (or delegate) and the Sponsor's Medical Monitor within the designated time frames. If the Investigator does not have all information regarding an SAE, he/she will not wait to receive additional information before notifying the Sponsor (or delegate) and the Sponsor's Medical Monitor of the event and completing the form/eCRF. The form/eCRF will be updated as soon as possible when additional information becomes available.

The Investigator will always provide an assessment of causality at the time of the initial report.

Completion of the SAE form/eCRF in an electronic data capture (EDC) system is the preferred method to transmit this information to the Sponsor (or delegate) and the Sponsor's Medical Monitor for SAE receipt. In rare circumstances, and in the absence of facsimile, computer and scanner equipment, notification by telephone is acceptable, with a copy of the SAE form sent by overnight mail. Initial notification via the telephone does not replace the need for the Investigator (or designee) to complete and sign the SAE form/eCRF within the outlined time frames.

Any event that in the opinion of the Investigator (or designee) may be of immediate or potential concern for the patient's health or well-being will be reported to the Sponsor's Medical Representative or emergency contact.

Adverse events will be classified as SUSARs if the AE or suspected adverse reaction meets the definition of "unexpected" in [Section 6.1](#). All SUSARs should be reported to the ethics committee and regulatory authority in accordance with applicable regulatory requirements for expedited reporting. It is the Sponsor's responsibility to report SUSARs to the ethics committee and regulatory authority.

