9.2.4. Suspension, Discontinuation, and Completion of the Study

The Sponsor reserves the right to suspend or discontinue the study or part of the study at any time for any reason. If the study is suspended or terminated, the Sponsor will ensure that applicable regulatory agencies and IRBs are notified as appropriate. Additionally, the discontinuation of a registered clinical study, which has been posted to a designated public website, will be updated accordingly. Should the study be terminated and/or a site closed, all IP pertaining to the study must be returned to the Sponsor or its representative.

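### For a study-level halt, protocol section 3.3.5 is stricter on repeated SAEs than 3.3.4, omits the life-threatening SAE, and ties its only single-event criterion to a rating that a death can rarely earn

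*Combined protocol and SAP*

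**What the plan says.** Section 3.3.4 (Withdrawal from Study) includes, among the reasons a patient may leave, termination or suspension of the whole study. Its first example is "study drug-related unexpected life-threatening serious AEs (SAEs) detected during safety monitoring (e.g., torsade de pointes or other ventricular arrhythmias"). Its second example concerns a recurring event and is worded as "2 or more of the same drug-related (possible or probable) treatment-emergent SAE".

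Section 3.3.5 (Criteria for Stopping the Study) lists four grounds on which the Sponsor, with the Medical Monitor, may stop:

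- "Occurrence of an SAE assessed as probably related to IP and resulting in death";
- at least two SAEs of one kind "that are determined to be clinically significant (CS) and assessed as probably related to IP";
- two or more cases of acute pancreatitis;
- two or more cases of acute hepatitis meeting Hy's Law.

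Both lists are introduced as examples and not as complete.

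Section 6.2.2 describes the Probable rating as "Clear temporal association with improvement on cessation of study drug or reduction in dose; reappears upon rechallenge or follows a known pattern of response". Possible needs only a reasonable temporal sequence and allows that the patient's clinical state or other therapies may be the cause.

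SAEs go to the Sponsor and Medical Monitor within 24 h under 6.6.2, and "The Investigator will always provide an assessment of causality at the time of the initial report". Section 9.2.4 adds: "The Sponsor reserves the right to suspend or discontinue the study or part of the study at any time for any reason".

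**The concern.** A reader who wants to know when the study should be halted will turn to 3.3.5 by its title. There they find a harder causality test for repeated SAEs than the protocol uses one section earlier, with an extra condition and no reason given. They also find no mention of the unexpected life-threatening SAE that 3.3.4 names. The one criterion that does not wait for a second event depends on a rating that a death is poorly placed to receive.

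Sections 1.1.4 and 1.2 describe one completed clinical study, in healthy volunteers dosed for up to 14 days. This trial doses patients for 28 days, twice as long (28 / 14 = 2). A first death rated possibly related, or a first drug-related torsade de pointes, would meet no criterion listed in 3.3.5. The Sponsor would know of it and could act, but the section meant to guide that decision would not name the event.

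**Working it through.** The plan gives no operating characteristic for these criteria, and section 8.1.4 states no formal hypothesis, so there is no figure to reproduce. The check is a comparison of text, followed by an illustration.

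**1. The two lists side by side**

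| Ground | 3.3.4 | 3.3.5 |
|---|---|---|
| Repeated SAE of the same kind | 2 or more; possible or probable | 2 or more; probable only, and clinically significant |
| Drug-related unexpected life-threatening SAE | Named, no number given | Not listed |
| Fatal SAE | Not listed separately | One event; probable only |
| Acute pancreatitis | Not listed | 2 or more |
| Hy's Law hepatitis | Not listed | 2 or more |

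Two SAEs of the same kind, both rated possible, match an example in 3.3.4 but not the repeated-SAE criterion in 3.3.5.

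**2. Counts in 3.3.5.** Four criteria are listed. One can be met by a single event, three need two or more, and two require a probable rating.

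**3. Can a death be rated Probable?** Section 6.2.2 offers three elements besides timing.

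- Improvement on cessation or dose reduction: a fatal event will rarely show this.
- Reappearance on rechallenge: not possible after a death.
- A known pattern of response: possible, but prior human experience as described is one healthy-volunteer study of up to 14 days. A new kind of reaction would not fit a known pattern.

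The punctuation leaves open whether a known pattern alone is enough. If every element is needed, a death could almost never qualify. If a known pattern suffices, it could qualify, but probably not often. How often cannot be settled here, because 6.2.2 relies on clinical judgment and on the investigator's brochure, which is not among the documents.

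**4. Illustration under assumed rates.** Planned SPR720 exposure is about n = 2 × 19 (sparse PK sites) + 2 × 6 (intense PK sites) = 50 patients (section 3.1). Let p be the true risk per patient of one kind of drug-related SAE and s the share rated probable. Neither is in the documents. With q = p × s,

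P(2 or more) = 1 − (1 − q)^50 − 50 q (1 − q)^49.

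| Assumed p | Possible or probable counts (q = p) | s = 75% | s = 50% | s = 25% |
|---|---|---|---|---|
| 2% | 0.26 | 0.17 | 0.09 | 0.03 |
| 4% | 0.60 | 0.45 | 0.26 | 0.09 |
| 6% | 0.81 | 0.66 | 0.45 | 0.17 |

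For example, p = 4% and s = 50% give q = 0.02 and 1 − 0.364 − 0.372 = 0.264. The clinical-significance condition is not modelled and could only lower the last three columns.

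For one kind of related, non-fatal, unexpected life-threatening SAE, the chance of exactly one case in 50 patients is 50 p (1 − p)^49. That is 30.6%, 37.2% and 20.2% at assumed risks of 1%, 2% and 5%. With exactly one such case, no criterion in 3.3.5 is met.

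**The case against.** The strongest reply is that two open lists of examples can differ without contradiction. Section 3.3.5 says the Sponsor may stop, and 9.2.4 allows suspension for any reason. The wording in 3.3.4 explains why a patient might leave the study and is not a stopping rule. Possible is a broad category in a disease for which section 1.1.2 cites 5-year mortality of 25% to 40%, so reserving a study-level stop for probable events is defensible. The point about deaths also depends partly on a brochure that is not available.

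Much of this stands, and it rules out several stronger readings that a reader might infer:

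- That the criteria prevent the Sponsor from stopping. They do not, for the reasons just given.
- That a first event would go unreviewed. Section 6.6.2 requires a report within 24 h with a causality rating, and section 6.7 lets the Sponsor ask for further investigation.
- That a death can never be rated Probable. The known-pattern route may be open.
- That the mismatch calls for a compulsory pause in randomization with a check of the treatment assignment. Meeting a 3.3.5 criterion compels no pause now, so the lack of one does not follow from the mismatch. Such a pause would be a design preference. A release message sent only for placebo patients would also reveal the assignment, which section 4.3 keeps from the Sponsor and sites apart from designated staff.

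What the reply does not explain is why the same decision carries two thresholds. The protocol already accepts possible events as a ground for a halt in 3.3.4. Because stopping is discretionary, naming the broader ground in 3.3.5 commits the Sponsor to nothing more than considering it.

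**Conclusion.** The concern holds as an inconsistency in a safety decision threshold. Section 3.3.5 asks for more than 3.3.4 on repeated SAEs, in both causality and clinical significance. It leaves out the unexpected life-threatening SAE, and its only single-event criterion fits poorly with the definition of Probable. The named criteria are inconsistent and too narrow, but they do not bar review or stopping.

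The size is textual: two of four criteria require a probable rating, and one of four can be met by one event. The binomial figures show only how the wording could matter if the assumed rates and rating shares were true; they are not evidence of an effect. The conclusion on deaths rests on reading 6.2.2 as written, without the investigator's brochure.

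**What to change.** In section 3.3.5:

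1. In the first two bullets, replace 'probably related to IP' with 'possibly or probably related to IP'. In the second bullet, also delete the clinical-significance condition, so that it matches 3.3.4. If the Sponsor prefers to keep 'probably' for deaths, state in 6.2.2 that the improvement and rechallenge elements do not apply to fatal events.
2. Add a bullet: 'Occurrence of an unexpected life-threatening SAE (for example, torsade de pointes) assessed as possibly or probably related to IP'. The single-event count is a choice, because 3.3.4 gives no number.

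In section 3.3.4, add a cross-reference to 3.3.5 after the SAE examples.

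The list then has five criteria. Two can be met by a single event, and none requires a probable rating alone, unless the Sponsor keeps it for deaths.

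The cost is protocol wording, with no added visits or samples. The downside is that some events due to underlying disease will meet a criterion and need consideration. So will some events on placebo: section 4.1 says "Investigational product refers to both SPR720 and placebo in this Investigational Product section", causality is rated blind, and one third of double-blind patients (25 of 75) receive placebo. The decision to stop remains with the Sponsor.
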